10.1.2 Serious Adverse Events

Each AE is to be classified by the Investigator as SERIOUS or NONSERIOUS. An AE that meets 1 or more of the following criteria/outcomes is classified as serious:

- Death
- Life-threatening (see paragraph below on life-threatening)
- In-patient hospitalization or prolongation of existing hospitalization (see paragraph below on hospitalization)
- Persistent or significant disability/incapacity (see paragraph below on disability)
- Congenital anomaly/birth defect
- Is considered a medically important event not meeting the above criteria, but which may jeopardize a subject, or may require medical or surgical intervention to prevent one of the criteria listed in this definition.

In addition to the above criteria for classifying AEs as serious, the following situations will also be classified as serious for purposes of this study:

- Dialysis or Transplantation – Events requiring transition to chronic, ongoing dialysis, or requiring an acute transient course of dialysis, or requiring an immediate kidney transplantation (ie, not pre-planned) will be classified as serious. Guidance for the reporting of these events is provided in [Section 10.1.1, Adverse Events](#).
- Malignancies – Newly diagnosed malignancies or a recurrence of a malignancy should be reported as an SAE with the seriousness criterion “medically important” if no other seriousness criteria are met. If a subject develops basal cell carcinoma of skin, squamous cell carcinoma of skin, or cervical carcinoma in situ during the study, or has worsening of these events from Baseline, the Investigator will determine if the event is reported as an AE or SAE.
- Designated Medical Events - The sponsor maintains a list of designated medical events (DME) that they will always classify as serious adverse events. If an event on the DME list is reported as an AE additional information on the event (e.g. investigator confirmation of seriousness, causality) will be requested from the Investigator.

Serious also includes any other event that the Investigator or Sponsor judges to be serious. If there is any doubt whether the information constitutes an AE or SAE, the information is to be treated as an SAE.

The Sponsor has a list of events that they classify as “always serious” events. If an AE is reported that is considered to be an event per this classification as “always serious”, additional information on the event may be requested.

Life-threatening – Any event in which the subject was at risk of death at the time of the event; “life-threatening” does not refer to an event which hypothetically might have caused death if it were more severe. For example, drug-induced hepatitis that resolved without evidence of hepatic failure would not be considered life threatening, even though drug-induced hepatitis of a more severe nature can be fatal.

Hospitalization – Hospitalization is defined as an overnight admission with observation of a minimum of 24 hours. A hospitalization planned before the start of the study for a pre-existing condition that has not worsened during the AE reporting period does not constitute an SAE unless an untoward event occurs related to the procedure (eg, elective hospitalization for a total knee replacement due to a preexisting condition of osteoarthritis of the knee that has not worsened during the course of the study).

Disability – Defined as a substantial disruption in a person’s ability to conduct normal life functions.

10.2 Eliciting Adverse Event Information

The Investigator is to report all directly observed AEs and all AEs spontaneously reported by the study subject. In addition, each study subject will be questioned about AEs at each visit following the initiation of treatment.

10.3 Reporting

Each AE is to be classified by the Investigator as SERIOUS or NONSERIOUS.

All AEs that occur in study subjects during the AE reporting period specified in the protocol must be reported, whether or not the event is considered related to study medication (vadadustat or darbepoetin alfa).

10.3.1 Reporting Period

The AE reporting period for this study begins from time of randomization through global study completion.

In addition, any AE that occurs subsequent to the AE reporting period that the Investigator assesses as related to the study medication should also be reported as an AE.

10.3.2 Reporting AEs

NONSERIOUS AEs are to be reported on the AE CRFs.

10.3.3 Reporting SAEs

Any SAE, regardless of causal relationship, must be reported to the Sponsor’s Medical Monitor or CRO designee within 24 hours after the Investigator becomes aware of the SAE. Compliance

with this time requirement is essential so that the Sponsor may comply with its regulatory obligations.

The initial SAE report should be completed as fully as possible but should contain, at a minimum:

- Subject number/ID, sex, and age/date of birth
- The date of report
- Name of the reporter
- Name of the suspected medicinal product
- A description of the event, including event term(s), seriousness criteria, and a clinical summary of the event
- Causality assessment.

Information about all SAEs (either initial or follow-up information) should be collected and recorded in English on the electronic SAE Report Form within the electronic data capture (EDC) system. The Investigator must assess the relationship to each specific component of the study medication. If the event meets serious criteria and it is not possible to access the EDC system, a paper SAE Report Form should be sent to the CRO via email or fax or the Investigator will call the CRO SAE hotline within 24 hours of being made aware of the SAE (reference the site manual for contact information). When the EDC system becomes available, the SAE information must be entered within 24 hours of the system becoming available.

The Investigator must report follow-up information relating to an SAE to the Sponsor's Medical Monitor or CRO designee within 24 hours of awareness by the Investigator by updating the electronic CRF with the new information or by submitting a paper SAE Report Form in the event that the EDC is not available. When the EDC system becomes available, the SAE information must be entered within 24 hours. The subject should be observed and monitored carefully until the condition resolves or stabilizes.

All deaths are to be thoroughly investigated and reported. Autopsy reports and death certificates are to be obtained, if possible.

The Sponsor and/or its designee are responsible for reporting SAEs to all applicable regulatory agencies and the central ethics committees within the required timeline.

The Investigators are responsible for submitting required safety information to their local Institutional Review Board (IRB) or Independent Ethics Committee (IEC) as per local regulations. This information includes, but is not limited to, any safety alert letter received from the Sponsor and any SAEs occurring at their investigative site.

10.3.4 Reporting Study Endpoints

Investigators will be counseled to report any event that they assess as potentially being a study endpoint requiring adjudication (death, myocardial infarction, stroke, thromboembolic events, and hospitalization for HF). All study endpoint events will be submitted blinded to the EAC for adjudication. To protect the integrity of the trial, already adjudicated events will not be unblinded or reported to either Health Authorities (HAs) or Investigators as safety reports unless otherwise requested by HAs or Ethics Committees. After study completion, these events will be included in the final analysis which will be unblinded and submitted to HAs with the study report.

10.3.5 Relationship to Study Medication

The causal relationship of the AE to study medication (vadadustat or darbepoetin alfa) will be assessed by both the Investigator and the Sponsor.

The assessment of causal relationship to study medication should be evidence-based, and not based on the premise that all AEs are possibly causally related to study medication until proven otherwise.

Examples of evidence that would suggest a causal relationship between the study medication and the AE include the occurrence of an AE that is uncommon and known to be strongly associated with drug exposure (eg, angioedema, hepatic injury, and Stevens-Johnson syndrome) or an AE that is uncommon in the population exposed to the drug.

The causal relationship of the AE is assessed using a binary system, and AEs are classified as either ‘related’ or ‘unrelated’:

Related: There is ‘reasonable possibility’ that the drug caused the AE. The AE follows a reasonable temporal sequence from the time of drug administration. There is supportive evidence (facts) to suggest a possible causal relationship, irrespective of the degree of certainty between the observed AE and the drug.

Unrelated: An AE does not follow a reasonable temporal sequence from administration of the product and/or there is no reasonable possibility that the drug caused the AE. This assessment includes situations where the AE is related to other factors such as the subject’s clinical state, other therapeutic interventions, or concomitant drugs administered to the subject.

Default assessments using the “related” category without supportive evidence for a causal relationship to study medication is generally uninformative and does not contribute meaningfully to the development of the safety profile of the drug or to subject protection.

Investigators are encouraged to choose the most plausible cause for the event(s) from the following list: medical history, lack of efficacy/worsening of treated condition, study medication, other treatment (concomitant or previous), withdrawal of study medication, administration error, protocol-related procedure, and others (specify).

10.3.6 Severity

The Investigator will assess each AE as either MILD, MODERATE, or SEVERE using the following guidelines to describe the maximum severity of the AE:

MILD: Does not interfere with subject's usual function

MODERATE: Interferes to some extent with subject's usual function

SEVERE: Interferes significantly with subject's usual function

Note that a **severe** AE is not necessarily a **serious** AE. For example, a headache may be severe in intensity, but would not be classified as serious unless it met 1 of the criteria for serious events listed above.

10.3.7 Follow-Up of Unresolved Events

All AEs should be followed until they are resolved or the Investigator assesses them as chronic or stable or the subject's participation in the trial ends (ie, until a final report is completed for that subject).

In addition, all SAEs and those nonserious events assessed by the Investigator as possibly or probably related to the study medication should continue to be followed even after the subject's participation in the trial is over. Such events should be followed until they resolve or until the Investigator assesses them as "chronic" or "stable". Resolution of such events is to be documented on the appropriate CRF.

10.4 Exposure In Utero

A pregnancy in a female subject must be confirmed by a positive serum β human chorionic gonadotropin (β -HCG) test.

The study medication should be immediately discontinued once the pregnancy of a female study participant has been confirmed.

If any study participant becomes or is found to be pregnant while receiving a study medication (vadadustat or darbepoetin alfa) or within 30 days of discontinuing the study medication, the pregnancy must be recorded on the Pregnancy Reporting Form/Exposure in Utero Form in EDC within 24 hours of awareness of the pregnancy or the Investigator will call the CRO SAE hotline within 24 hours of being made aware of the pregnancy.

Pregnancy during this time frame of the female partner of a male subject should also be reported.

The Pregnancy Reporting Form/Exposure in Utero Form must be completed with all known information regarding the pregnancy at the time of reporting. Investigative site personnel will update the form with additional information regarding the pregnancy and the outcome of the pregnancy as it becomes available until the outcome of the pregnancy is reported.

The Investigator will follow the subject (or female partner of a male subject) until completion of the pregnancy. If the outcome of the pregnancy meets the criteria for classification as a SAE (ie, spontaneous abortion, stillbirth, neonatal death within 1 month of birth, or congenital anomaly [including that in an aborted fetus]), the Investigator will also follow the procedures for reporting a SAE within 24 hours of awareness. A pregnancy in and of itself is not considered an AE; however, unexpected complications are considered AEs.

Additional information about pregnancy outcomes follows:

- Note that "spontaneous abortion" includes miscarriage and missed abortion.
- All neonatal deaths that occur within 1 month of birth should be reported, without regard to causality, as SAEs. In addition, any infant death after 1 month that the Investigator assesses as related to the in utero exposure to the study medication should also be reported.
- In the case of a live birth, the "normality" of the newborn can be assessed at time of birth.
- The "normality" of an aborted fetus can be assessed by gross visual inspection unless there are pre-abortion laboratory findings suggestive of a congenital anomaly.

10.5 Special Situations

Certain safety events, called ‘Special Situations’, that occur in association with study medication(s) may require reporting. These Special Situations include, but are not limited to, the following:

- Overdose of the medicinal product
 - Darbepoetin Alfa Overdose: The PI or SmPC should be referenced for information on darbepoetin alfa overdosing.
 - Vadadustat Overdose: There is no known antidote for vadadustat. In cases of suspected overdose, Subjects should be treated per standard medical practice based on the Investigator’s judgment and dose delays and reductions may be implemented as necessary.

Chronic overdosage with vadadustat may result in excessive production of red blood cells and polycythemia. Polycythemia can be potentially life threatening and may result in severe thrombosis and death (known as hyperviscosity syndrome). If hyperviscosity syndrome is observed, vadadustat should be discontinued and standard treatment for polycythemic hyperviscosity syndrome should be initiated (i.e., phlebotomy).

- Suspected abuse/misuse of the medicinal product
- Inadvertent or accidental exposure to the medicinal product
- Medication error involving the medicinal product (with or without subject/patient exposure to the Sponsor medicinal product, eg, name confusion)
- Drug-drug interaction.

Special situations should be reported on the Special Situations CRF whether they result in an AE/SAE or not. Special situations with associated AE/SAE should also be reported on the corresponding AE/SAE forms, following applicable AE or SAE process.

11 DATA ANALYSIS

Data collected throughout the study will be summarized using descriptive statistics and listed in by-subject listings. Continuous variables will be summarized using number of subjects with data, mean, standard deviation, median, minimum, and maximum. For categorical variables, the number and percentage of subjects in each category will be tabulated. Summaries will be provided by treatment group within appropriate analysis populations (as defined in [Section 11.2, Study Analysis Populations](#)) and by time point/time period as appropriate.

For Hb, Baseline will be calculated as the average of the central laboratory Hb measurements of samples taken at the screening visit closest to the date of randomization and the measurement taken at randomization.

For other parameters, unless otherwise specified, Baseline will be defined as the last available value prior to the first dose of study medication.

Hemoglobin values as assessed through the central laboratory will be used for efficacy and safety evaluations; local HemoCue Hb values will be used only for dose adjustments.

11.1 Sample Size Determination

The goal of this study is to demonstrate the efficacy and safety of vadadustat compared with darbepoetin alfa for the correction and maintenance of Hb in subjects with anemia secondary to NDD-CKD. The sample size is calculated to ensure sufficient power for testing both efficacy in this trial and the primary safety endpoints as part of a pooled analysis.

11.1.1 Sample Size for the Primary Efficacy Endpoint

The primary efficacy endpoint is defined as the mean change in Hb from Baseline (mean pretreatment Hb) to the average Hb over the primary evaluation period (mean Hb from Weeks 24-36).

The primary efficacy objective of this study is to show that vadadustat is noninferior to darbepoetin alfa within the noninferiority margin. Noninferiority will be established based on a margin of -0.75 g/dL (for vadadustat minus darbepoetin alfa).

For the primary efficacy analysis in this study, it is assumed that the mean change from Baseline in Hb for vadadustat will be the same as for darbepoetin alfa, and the common standard deviation for the mean change from Baseline is assumed to be 1.5 g/dL. Noninferiority will be established based on a 2-sided 95% confidence interval for the difference between the vadadustat group and darbepoetin alfa and using a noninferiority margin of -0.75 g/dL. With these assumptions and approximately 925 subjects per treatment group for the primary efficacy analysis, the noninferiority assessment will have >90% power.

11.1.2 Sample Size for the Primary Safety Endpoint

The primary safety endpoint is the time from randomization date to the first (adjudicated) MACE +1.

The primary safety analysis will be based upon all events that accrue over the 2 NDD-CKD studies (Studies AKB-6548-CI-0014 and AKB-6548-CI-0015). The sample size with respect to the MACE endpoint has been determined based on the number of events needed to demonstrate noninferiority of the 2-sided 95% confidence interval for the hazard ratio (vadadustat/darbepoetin alfa). It has been calculated that 631 events will be required overall to have 80% power to establish noninferiority with a margin of 1.25, and >90% power to establish noninferiority with a margin of 1.3 assuming no difference between treatment groups. The power is >90% to establish a noninferiority margin of 1.25 if the hazard ratio is 0.95 favoring vadadustat. A MACE rate of 10% annually is anticipated in both treatment arms based on a comprehensive review of available epidemiology and prospective clinical studies in the field. The number of MACE in each study will be a function of the actual pattern and size of enrollment as well as the duration of follow-up.

11.2 Study Analysis Populations

The following analysis populations will be used in this study:

- Randomized population: defined as all randomized subjects
- Full analysis population: defined as randomized subjects receiving 1 or more doses of study medication and had at least one Hb assessment during the primary efficacy evaluation period. This population will be analyzed based upon the randomized treatment.

- Per protocol (PP) population: defined as all randomized subjects who received study medication (vadadustat or darbepoetin alfa) during the primary evaluation period, had at least 2 Hb assessments during the primary evaluation period, and received no rescue therapy (with ESA or RBC transfusion) in the 8 weeks prior to the evaluation period, and have no protocol deviations affecting the primary endpoint analyses. Protocol deviations leading to exclusion from the per protocol population will be specified prior to database lock on a blinded basis and recorded in a separate document.
- Safety population: defined as all subjects who received at least 1 dose of study medication. This population will be analyzed based upon the actual treatment received.

Efficacy analyses will utilize the randomized, full analysis, and PP populations while safety analyses (including MACE) will utilize the randomized population.

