5.3 Secondary Efficacy Endpoints

The key secondary efficacy endpoints include the following:

- Mean change in Hb value between Baseline (mean pretreatment Hb) and the secondary evaluation period (Weeks 40-52)
- Proportion of subjects with Hb values within the target range during the primary evaluation period (Weeks 24-36)
- Proportion of subjects with Hb values within the target range during the secondary evaluation period (Weeks 40-52)

Other secondary efficacy endpoints include:

- Proportion of time with Hb values within the target range during the primary evaluation period (Weeks 24-36)
- Proportion of time with Hb values within the target range during the secondary evaluation period (Weeks 40-52)
- Proportion of subjects with Hb increase of >1.0 g/dL from Baseline
- Time to achieve Hb increase of >1.0g/dL from Baseline

- Mean change in Hb between Baseline (mean pretreatment Hb) and the primary evaluation period (mean Hb from Weeks 24-36) stratified by pre-baseline ESA exposure
- Progression of CKD
- Proportion of subjects receiving IV iron therapy from Baseline to Week 52
- Mean monthly dose of IV elemental iron administered from Baseline to Week 52 in subjects who have received IV iron
- ESA rescue
- Dose adjustments from Baseline to Week 52
- Proportion of subjects receiving RBC transfusion(s) from Baseline to Week 52

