11.5 Missing Data

Subjects who stop study medication treatment after randomization and prior to completion of the study should continue with planned study visits and assessments unless they withdraw consent for participation in the study. Similarly, subjects will continue with study medication and study procedures following the initiation of rescue therapy, with the exception that the subjects must discontinue taking study medication while receiving an ESA rescue therapy. Treatment with study medication should be resumed after an appropriate interval following the ESA rescue therapy as described in [Section 8.4.7, Rescue Therapy](#). Data will continue to be collected following initiation of the rescue therapy as per the study Schedule of Activities.

All data collected during the study, including at any point after the initiation of rescue therapy as well as after early discontinuation of study medication treatment, will be used for the primary analysis as well as main analyses of all efficacy endpoints. Sensitivity analyses will be performed to assess an impact of rescue therapy on study conclusions.

In the primary analysis of the primary efficacy endpoint, all available qualifying Hb measurements during the pretreatment period and during the primary evaluation period

(Weeks 24-36) will be used to calculate an average Hb during each period, respectively, for each subject. For any subject with no available Hb measurements during the primary evaluation period, multiple imputations will be used to impute the change from Baseline value (details are provided in the SAP). In an analogous manner, an average Hb will be calculated for the secondary evaluation period (Weeks 40-52) for each subject. Given the design of this study where the subjects will continue to be assessed after early study medication discontinuation, it is expected that there will be only a minimal amount of missing data and the primary analysis should not be substantially affected by the imputation.

All data pertaining to the MACE endpoint collected at any point during the study, both during study medication treatment and post study medication treatment discontinuation, and regardless of the rescue therapy, will be used for the primary analysis of the MACE endpoint and its individual components.

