11.6.2 Secondary Efficacy Analyses

Secondary efficacy endpoints analyses will be performed using the randomized and full analysis populations and the assigned treatment as described in [Section 11.2, Study Analysis Populations](#). Analysis for the key secondary efficacy endpoints will be repeated using the PP population with the actual treatment received.

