11.6.2.1 Key Secondary Efficacy Analyses

Mean change in Hb value between Baseline and the secondary evaluation period (Weeks 40-52) will be analyzed using the same methodology as specified for the primary efficacy endpoint. Sensitivity analyses similar to those of the primary efficacy endpoint will be performed and details will be provided in the SAP.

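### The only per-protocol population is anchored to Weeks 24-36, yet it is reused for two key secondary endpoints measured in Weeks 40-52

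*Protocol*

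**What the plan says.** Section 11.2 of the current protocol (Amendment 7, Version 8) has a single PP definition. It takes those randomized "who received study medication (vadadustat or darbepoetin alfa) during the primary evaluation period, had at least 2 Hb assessments during the primary evaluation period", who also "received no rescue therapy (with ESA or RBC transfusion) in the 8 weeks prior to the evaluation period" and have no protocol deviation bearing on the primary endpoint analyses. The list of excluding deviations is left to a separate document written blind before database lock; the other criteria are stated in full.

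Section 11.6.2 sets the use of this population: "Analysis for the key secondary efficacy endpoints will be repeated using the PP population with the actual treatment received".

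Section 5.3 lists three key secondary endpoints. Two belong to the secondary evaluation period, Weeks 40-52: the mean Hb change and the proportion of subjects in the target range. The third, also an in-target proportion, belongs to Weeks 24-36. Section 6.1 sets the two evaluation periods as Weeks 24-36 and Weeks 40-52.

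For the Weeks 40-52 mean change, Section 11.5 says: "In an analogous manner, an average Hb will be calculated for the secondary evaluation period (Weeks 40-52) for each subject". Section 11.6.2.1 says that the endpoint "will be analyzed using the same methodology as specified for the primary efficacy endpoint", and adds: "Sensitivity analyses similar to those of the primary efficacy endpoint will be performed and details will be provided in the SAP".

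**The concern.** In a noninferiority trial the PP repeat is a check on whether off-drug data or other active treatment pull the arms together. It can do this for Weeks 40-52 only if membership depends on what happened in, or shortly before, those weeks. Here membership is settled by an earlier window. The label then promises subjects treated and measured as planned in Weeks 40-52, and the rule does not check that.

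The error runs both ways. Subjects who are off drug or unmeasured in Weeks 40-52 are kept, and some who were treated and measured there are dropped. At stake is the meaning of two supportive analyses, not the primary conclusion.

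**Working it through.** **The plan's own figure.** Section 11.1.1 gives 925 subjects per arm, SD 1.5 g/dL, margin 0.75 g/dL, a two-sided 95% interval and no true difference. SE = 1.5 × √(2/925) = 0.0697, and 0.75/0.0697 − 1.96 = 8.8, so power is essentially 100%. The stated power above 90% is reproduced. The number per arm for 90% power is 2 × 1.5² × (1.960 + 1.282)² / 0.75² = 84.06, so 85.

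**Windows.** Appendix A schedules four Hb visits in Weeks 24-36 (24, 28, 32, 36) and four in Weeks 40-52 (40, 44, 48, 52). The windows share no visit. The rescue look-back starts at 24 − 8 = Week 16 and ends 40 − 24 = 16 weeks before the secondary period opens.

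| PP criterion in 11.2 | What it checks | What it checks for Weeks 40-52 |
|---|---|---|
| Study medication | Weeks 24-36 | nothing |
| At least 2 Hb values | 2 of 4 visits in Weeks 24-36 | 0 of 4 visits |
| No rescue | Weeks 16-24 | nothing after Week 24 |
| Deviations | effect on the primary endpoint | not addressed |

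**Three subjects traced through the text.**

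1. A subject takes drug at Week 24, stops soon after, has two Hb values by Week 36 and moves to a standard-of-care ESA. Section 7.5.5.2 provides for that treatment and Section 8.5.2 permits the ESA after permanent discontinuation, so it need not be a deviation. The subject is in the PP set for Weeks 40-52.
2. A subject meets the Weeks 24-36 criteria and has no Hb value in Weeks 40-52. Section 11.5 wants planned visits to continue after stopping drug, but Section 7.5.5.4 makes them flexible. The subject is still in the PP set. For the mean change, the primary methodology includes multiple imputation (11.6.1.1), so this subject's value may be entirely imputed.
3. A subject is rescued in Week 20, resumes study drug and has all four Hb values on drug in Weeks 40-52. The subject is excluded.

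**Why a repaired set needs two treatments of rescue.** The protocol gives no rescue rates, so the following inputs are assumptions. Let p be the excess proportion rescued on vadadustat, L the Hb lift from rescue, r the observed mean of rescued subjects, and 10.5 g/dL the mean of all others. Relative to the difference had nobody been rescued:

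- keeping observed values shifts the difference by p × L;
- deleting rescued subjects shifts it by p × (10.5 − r + L).

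With p = 0.10, L = 1.0 and r = 9.5, the no-rescue difference is 0.10 × (8.5 − 10.5) = −0.20. Keeping observed values gives 0.10 × (9.5 − 10.5) = −0.10, and deletion gives 0. Over p = 0 to 0.10 and L = 0.5 to 1.5, keeping shifts by 0 to 0.15 g/dL. At p = 0.10 and r = 9.0 to 10.0, deletion shifts by 0.10 to 0.30 g/dL. Both are zero if the arms are rescued equally, and both change sign if the excess is on darbepoetin alfa.

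**Precision of a smaller set.** The 95% half-width is 1.96 × 1.5 × √(2/n): 0.137 g/dL at n = 925 per arm and 0.170 at an assumed n = 600.

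**The case against.** The strongest reply is that nothing is decided on this analysis. The primary conclusion uses the randomized population with post-rescue data kept by design (11.6.1.1). The key secondary endpoints are analysed in the randomized and full analysis populations, and PP is a repeat. This stands, and it sets the weight of the point.

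Second, entirely imputed values have partial cover. Section 11.6.1.2 lists an analysis restricted to subjects with available Hb data, and 11.6.2.1 promises similar analyses for the Weeks 40-52 mean change. This also stands, but it does not repair membership of the PP set.

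Third, a single set lets the two periods be compared in the same subjects. That is a fair use, but a different one from a per-protocol estimate for Weeks 40-52.

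Four stronger readings are tempting and not supported:

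- **Inflated false noninferiority.** If the true difference sat at −0.75 and a fraction f of 925 vadadustat PP subjects had the comparator mean, the one-sided rate would be 1 − Φ(1.96 − 0.75f/0.0697), which is 0.078 at f = 5% and 0.188 at f = 10%, against 0.025. The protocol states no PP decision rule for Weeks 40-52, and the figures assume switching in one arm only.
- **Early closure empties the PP set.** Section 7.5.1 lets the study end once all subjects have had the opportunity for Visit 13 (Week 36). That would remove Weeks 40-52 data from every population, and whether it happens depends on when the MACE accrue.
- **Missing sensitivity analyses for the Weeks 40-52 in-target proportion.** Such detail is commonly left to the SAP, so its absence here shows nothing.
- **Rescue inside Weeks 24-36 is unscreened in the primary PP analysis.** This is a separate matter, and the rescue-imputation analysis in 11.6.1.2 addresses it.

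**Conclusion.** The mismatch is established from the text alone: one PP set, anchored to the primary evaluation period, is applied to two endpoints in a window that does not overlap it. It is not a gap left to the SAP, because 11.2 states the criteria and 11.6.2 applies them.

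The impact is minor. Neither the size nor the direction of any bias can be derived from the protocol; the shifts shown above rest wholly on assumed rescue differences, and their range includes zero. The PP results for Weeks 40-52 simply would not describe what their label says. The full analysis population also requires an Hb value only in the primary period, so the randomized population is the only one of the three efficacy sets free of this anchoring.

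**What to change.** In 11.2, add a PP set for the two Weeks 40-52 endpoints with the same criteria re-anchored: study medication in Weeks 40-52, at least 2 Hb values in Weeks 40-52, and no deviation affecting those endpoints. Cite it in 11.6.2.

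Report this PP result in two ways:

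- with the sponsor's own 8-week rescue look-back moved to before Week 40 (Weeks 32-40);
- without that exclusion, handling rescue-affected Hb values as in the rescue-imputation analysis of 11.6.1.2.

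Both are needed because excluding rescued subjects can itself favour noninferiority. Give the numbers affected per arm, and read the result beside that of the randomized population.

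The cost is one definition, one cross-reference and a further supportive analysis, with no new data and no change to clinical management. The downside is a somewhat smaller and more selected set, since it keeps subjects still on drug in Weeks 40-52. The loss of precision is tolerable: even 600 per arm is far above the 85 that would give 90% power under the plan's assumptions.
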